Optimizing the postoperative recovery of arthroplasty patients is a key factor in the fast-track protocols and day-case initiatives. Investigations of the postoperative course after hip and knee arthroplasty has identified insufficient mobilization, muscle weakness and urinary retention to be frequent postoperative challenges. Especially early mobilization is crucial in achieving timely discharge and reducing the risk of thromboembolic events. These postoperative challenges can be related to the anaesthesia methods used in hip and knee arthroplasty, however, our knowledge on this subject is lacking.

Comparative studies between spinal anaesthesia (SA) and general anaesthesia (GA) suggest that GA may result in reduced length of stay, earlier mobilization, and less pain, while SA offers quicker post-anaesthesia care unit (PACU) discharge and less immediate postoperative pain. The choice between SA and GA lacks consensus among surgeons, with preferences varying based on individual or centre preferences. This current knowledge gap highlights the necessity for contemporary, detailed studies to inform optimal anaesthesia choices for hip and knee arthroplasty patients.

OBJECTIVES

The primary objective of this study is to compare the impact of spinal anaesthesia and general anaesthesia on early mobilization after total hip (THA), total knee (TKA) and unicompartmental knee arthroplasty (UKA).

Secondary objectives are to compare fulfilment of discharge criteria, postoperative nausea and vomiting, pain, and use of opioids after THA, TKA, and UKA anaesthetized using either SA or GA.

STUDY METHODS

TRIAL DESIGN

This study consists of three individual trials. Each trial examines different hip and knee arthroplasty populations, but has identical methods for inclusion, randomization, data collection and statistical analysis. The trials are named:

- Randomized trial on Spinal Anaesthesia vs. General Anaesthesia (SAGA) on recovery after total hip arthroplasty (RCT SAGA THA)
- Randomized trial on Spinal Anaesthesia vs. General Anaesthesia (SAGA) on recovery after total knee arthroplasty (RCT SAGA TKA)
- Randomized trial on Spinal Anaesthesia vs. General Anaesthesia (SAGA) on recovery after unicompartmental knee arthroplasty (RCT SAGA UKA)

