 - Motor control criteria: Poor muscle control or strength, insecure foot placement, impaired sensibility.

Stepwise mobilization course:

- Orthostatic test: from lying to sitting position.
- Motor control test: ability to move toes and lower limbs, firmly and securely planting the feet in the ground.
- Mobilization test: a few steps with a high walking frame.
- 5-Meter walking test using two crutches.

KEY SECONDARY OUTCOMES:

The key secondary outcomes are based on the first public registration of the study on https://euclinicaltrials.eu/ (2022-501221-21-00). Any erroneous disagreement between this first registration and the following registrations are corrected to coincide with the first registration.

Fulfilment of discharge criteria at 6 hours postoperatively:

v. 1.0

Fulfilment of functional discharge criteria is evaluated at both 4 and 6 hours postoperatively. This will be a dichotomous outcome where patients are either ready for discharge (fulfil all criteria) or are not ready for discharge (fail at least one criteria).

Pain levels at 4 and 6 hours postoperatively:

Pain levels (numerical relation scale (NRS) 0-10) during rest and activity (walking 5 meters) at 4 and 6 hours are registered through a nurse-assisted questionnaire.

Opioid use in Morphine Milligram Equivalents within the first 6 hours of surgery:

A cumulated amount of opioid in Morphine Milligram Equivalents within the first 6 hours postoperatively. Data on opioid use at the postoperative care unit and the bed ward is collected until 6 hours postoperatively.

Postoperative Nausea and Vomiting (PONV) at 4 and 6 hours postoperatively:

Nausea and vomiting levels (NRS 0-10) during rest and activity (walking 5 meters) at 4 and 6 hours are registered through a nurse-assisted questionnaire.

OTHER SECONDARY OUTCOMES:

Urinary retention: no spontaneous urination and bladder scan with >800 mL (>600 mL at Vejle) prior to discharge.

Vital signs: systolic and diastolic blood pressure, pulse, blood oxygen saturation, temperature. Postoperative blood sample results: Haemoglobin, serum-creatinine, and C-reactive protein. Opioid-Related Symptom Distress Scale – questionnaire (ORSDS): A score based on 20 opioid related symptoms evaluating the burden of these symptoms.

v. 1.0

Quality of Recovery – 15 score (QoR-15): a score based on 15 questions evaluating postoperative recovery.

3-minute Diagnostic Interview – Confusion Assessment Method (3D-CAM):

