Attitude towards anaesthesia type: Whether patients would like to receive similar anaesthesia for any following arthroplasty surgery.

Blood transfusions: Whether patients received blood transfusion.

Emergency room contacts, complications, readmission or mortality within 30 days of surgery.

ANALYSIS METHODS

The primary analysis aim is to assess whether the ability to be safely mobilized within 6 hours of hip and knee arthroplasty is different between the two anesthetic methods, GA and SA. The main hypothesis to be tested is that GA patients are more likely to be safely mobilized compared to SA patients within 6 hours of arthroplasty surgery. This will be assessed in the (mITT) population, defined as all patients having undergone the intended arthroplasty surgery, between the comparison groups (GA and SA) as allocated. Superiority of GA over SA in achieving safe mobilization within 6 hours of surgery will be claimed if a difference in proportions of 30% is found in favour of GA.

Main analysis of primary outcome: The proportion of patients able to be safely mobilized within 6 hours of surgery will be compared between intervention groups using a logistic regression model. A supporting model adjusted, including possible confounders such as age and sex, will also be conducted. Estimates from the analysis will be presented as odd-ratios and 95% confidence intervals, for both crude and adjusted models.

In case of cross-over cases, a per-protocol analysis with similar statistical methods will be conducted.

Key secondary continuous outcomes will be analysed using t-test or Wilcoxon rank-sum test depending on normality. Results from t-tests will be presented as differences in means and 95%

confidence interval. Results from Wilcoxon rank-sum tests will be presented as differences in medians and p-values. Key secondary dichotomous outcomes will be compared using fisher's exact test. A mixed-effect model accounting for repeated measures using patient ID as a random effect will be used to compare both 4 and 6 hours NRS scores for pain and PONV between the intervention groups.

Normality will be evaluated using quantile-quantile plots and histograms.

MISSING DATA

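### The effect measure for continuous key secondary outcomes is left to a look at plots, so it is not fixed in advance and can differ between the three trials

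*SAP*

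**What the plan says.** Four parts of the SAP bear on this.

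- **Analysis Methods, the rule.** "Key secondary continuous outcomes will be analysed using t-test or Wilcoxon rank-sum test depending on normality". Further on: "Normality will be evaluated using quantile-quantile plots and histograms". The SAP gives no threshold and no assessor. It does not say whether the plots are drawn per arm, pooled, per time point or per trial.
- **Analysis Methods, the output.** The t-test branch reports a difference in means with a 95% confidence interval. For the other branch: "Results from Wilcoxon rank-sum tests will be presented as differences in medians and p-values".
- **Analysis Methods, a further model for pain and PONV.** "A mixed-effect model accounting for repeated measures using patient ID as a random effect will be used to compare both 4 and 6 hours NRS". The sentence goes on to name these two outcomes. This model does not depend on the normality check.
- **Trial Design.** Each of the three trials "has identical methods for inclusion, randomization, data collection and statistical analysis".

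The outcomes concerned are defined under Key Secondary Outcomes. Opioid use is "A cumulated amount of opioid in Morphine Milligram Equivalents within the first 6 hours postoperatively". Pain is "Pain levels (numerical relation scale (NRS) 0-10) during rest and activity (walking 5 meters) at 4 and 6 hours", and PONV is scored on the same 0–10 scale, under the same conditions and at the same times. Confidence Intervals and P-values says that results come with 95% intervals and that multiplicity is not adjusted for.

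**The concern.** A mean difference and a median difference are different quantities. If plots of the outcome data decide which one is published, two analysts who both follow the SAP can report different effects from the same data. The same outcome can also appear as a mean difference in one trial and a median difference in another. Readers will naturally set the hip, knee and unicompartmental results beside each other, and the text invites this by calling the analyses identical.

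Two reporting faults come with the rule. The Wilcoxon branch gives no confidence interval, although the SAP promises one for its results. It also pairs the rank-sum test with a difference in medians, which is not what that test tests.

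Little is gained by waiting for the data. The scales are known now: NRS scores take whole values from 0 to 10, and cumulative opioid dose cannot be negative.

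**Working it through.** **Inputs.** The SAP gives no figure for the continuous key secondary outcomes, so there is none to reproduce on this point. Its arm sizes are used: 32 needed and 37 recruited. The 32 reproduces for 60% versus 90% (two-sided 5%, 80% power, pooled variance): [1.96·√(2·0.75·0.25) + 0.842·√(0.6·0.4 + 0.9·0.1)]² / 0.30² ≈ 31.5, rounded up to 32.

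**Assumptions.** The SAP states no outcome distributions, so four were assumed:
- normal;
- pain as N(4, 2.2) rounded and limited to 0–10;
- PONV with 70% zeros and otherwise uniform on 1–10;
- MME with 20% zeros and otherwise log-normal (log mean 2.7, log SD 0.8).

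A visual check cannot be simulated, so a Shapiro-Wilk test at 5% on within-arm residuals stands in for it.

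**Step 1: can the trials end with different tests?** Let q be the chance that one trial is sent to Wilcoxon. If the check is made per trial and q is the same in each, the chance that the three do not all agree is 1 − q³ − (1−q)³ = 3q(1−q). At 32 per arm:

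| Assumed outcome | q | 3q(1−q) |
|---|---|---|
| Normal | 0.050 | 0.14 |
| Pain NRS, rounded | 0.223 | 0.52 |
| PONV, 70% zeros | 1.000 | 0.00 |
| MME, strongly skewed | about 1.00 | about 0.00 |

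At 37 per arm the figure is about 60% for pain and 0% for strongly skewed MME; for an assumed mildly skewed MME it is about 30%. The formula cannot exceed 3 × 0.5 × 0.5 = 0.75. The answer therefore depends on a shape that the SAP does not give.

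**Step 2: does the effect measure matter?** Take PONV with 70% zeros in one arm and 55% in the other, non-zero scores uniform on 1–10 (mean 5.5).
- Mean difference: (0.45 − 0.30) × 5.5 = 0.825 (simulated 0.82).
- Median difference: both medians are 0, so it is 0.
- What the rank-sum test addresses is P(Y>X) + ½P(Y=X), with Y the 55% arm. P(Y>X) = 0.45×0.70 + ½×(0.45×0.30×0.9) = 0.315 + 0.061 = 0.376. P(Y=X) = 0.55×0.70 + 0.45×0.30×0.1 = 0.385 + 0.0135 = 0.3985. The sum is 0.376 + 0.199 = 0.575, against 0.5 under no effect.

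The Wilcoxon branch could thus report a small p-value beside an effect of zero, with no interval.

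**Step 3: does the rule disturb the 5% level?** Null simulation, 8,000 trials per setting, 32 per arm (Monte Carlo standard error √(0.05×0.95/8000) = 0.0024):

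| Assumed outcome | t-test always | Wilcoxon always | Choice by normality | Smaller p-value |
|---|---|---|---|---|
| Normal | 0.052 | 0.047 | 0.052 | 0.060 |
| Pain NRS | 0.047 | 0.047 | 0.048 | 0.055 |
| PONV | 0.048 | 0.046 | 0.046 | 0.061 |
| MME | 0.044 | 0.048 | 0.048 | 0.065 |

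At 37 per arm the choice by normality gives 0.048–0.052 and the smaller p-value 0.059–0.064.

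**The case against.** The strongest reply has four parts.

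- **Error rate.** A reader might infer that a data-dependent choice of test inflates the 5% level. The documents do not support this. The rule depends on the shape of the distribution, not on the results, and the normality-based choice stays near 5%. Only picking the smaller p-value raises it, and the SAP does not provide for that. The SAP also makes no multiplicity adjustment, so it claims no familywise control here. This part stands in full.
- **Scope.** A reader might infer that every continuous key secondary outcome hangs on the plots. It does not: pain and PONV also have a mixed-effect model that is not conditional on normality. This stands. What remains for these two outcomes is that the SAP plans two analyses and names neither as leading.
- **Identical methods.** One rule applied to three trials is arguably one method, and the SAP plans no pooling or comparison across trials. This stands so far as to rule out a flat contradiction. The same rule can still yield different effect measures.
- **Likelihood.** If MME is strongly skewed, Wilcoxon is chosen in all three trials and the split does not arise. This also stands, but it shows as well that fixing the method now costs next to nothing. The missing interval and the ill-matched median difference would then apply in every trial.

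**Conclusion.** The point holds as a minor one. The SAP does not fix the test or the effect measure for opioid use, and it does not name the leading analysis for pain and PONV. The three trials can therefore report different measures for the same outcome. How likely that is ranges from about 0% to about 50–60% under the assumptions shown; those percentages rest on invented distributions and on a formal test in place of a visual check. Three things need no assumption: the absence of a threshold, the missing confidence interval in the Wilcoxon branch, and the mismatch between a difference in medians and the rank-sum test.

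The point does not rest on type I error, which is essentially unaffected, and no primary conclusion depends on it. Nor does it follow that a t-test would be wrong for these outcomes: in the simulation it held its level throughout. What matters is that the choice is made before the data are seen.

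**What to change.** In Analysis Methods, delete the clause that makes the test conditional on normality, and the sentence on plots and histograms. Then:

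1. **Opioid use.** State one method and one effect measure for all three trials, for example the Wilcoxon rank-sum test with the Hodges-Lehmann shift and its 95% confidence interval. Drop the difference in medians.
2. **Pain and PONV.** Name the repeated-measures mixed model as the leading analysis, with between-group differences at 4 and at 6 hours and their 95% confidence intervals, for rest and activity separately. The Hodges-Lehmann shift is less useful for PONV: in the example above 39.85% of pairs are tied and 100 − 37.6 − 39.85 = 22.6% are negative, so the median pairwise difference is again 0.
3. **All three trials.** State that these choices apply in each trial whatever the distributions look like.

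The cost is SAP wording only. The downside is a loss of about 5% in efficiency against the t-test for opioid use if that outcome turns out to be normal.

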If one centre experiences recruitment issues, randomisation envelopes in 1 or 2 blocks will be transferred to the other centre.

FRAMEWORK

Superiority of GA over SA in achieving safe mobilization within 6 hours of surgery will be claimed if a difference in proportions of 30% is found in favour of GA.

STATISTICAL INTERIM ANALYSES AND STOPPING GUIDANCE

No interim analyses are planned. The investigators will evaluate the occurrence of serious adverse events, and if these occur in an unexpectedly high proportion of patients in relation to one of the interventions, the study will be stopped.

TIMING OF FINAL ANALYSIS

The final analysis is conducted when all included patients in the trial have passed the last followup (30 days after surgery).

TIMING OF OUTCOME ASSESSMENTS

Primary endpoint: safe mobilization at 5-meter walking test within 4-6 hours postoperatively. Patients will be given until 6 hours postoperatively to complete the walking test, and any early failed attempts will be redone at 6 hours postoperatively.

Secondary endpoints: fulfilment of discharge criteria, postoperative nausea and vomiting, pain, and use of opioids are evaluated at 4 and 6 hours postoperatively on the day of surgery and at 10:00 and 18:00 on any following postoperative days if the patient is still admitted.

STATISTICAL PRINCIPLES

CONFIDENCE INTERVALS AND P-VALUES

Confidence level is set at 95%, and results are presented with 95% confidence intervals. No adjustments for multiplicity are made.

ADHERENCE AND PROTOCOL DEVIATIONS

If patients are anaesthetised differently than allocated (i.e., GA instead of SA, due to technical difficulties), this is registered, and data collection continues. Reasons for cross-over are registered and reported. The overall adherence within the intervention groups will be reported.

All protocol deviations regarding sample size, eligibility, randomization, intervention, outcome definitions and statistical analyses plan will be reported.

ANALYSIS POPULATIONS

Any cases of crossover between the intervention groups will be included in their allocated treatment group as part of a modified intention-to-treat (mITT) analysis. The mITT will exclude randomised patients that did not undergo the intended arthroplasty surgery in the SAGA setup:

- Patients that after randomisation, but before being told their treatment allocation, decided not to go through with the arthroplasty surgery at the hospital.

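### Wilcoxon results are to be reported as a difference in medians with a p-value and no confidence interval, against the SAP's own rule; this matters most for opioid use

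*SAP*

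**What the plan says.** The SAP section on confidence intervals and p-values sets a general rule: "Confidence level is set at 95%, and results are presented with 95% confidence intervals". It makes no exception.

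The section on analysis methods then goes test by test. The primary logistic model is reported as odds ratios with 95% CIs. For the secondary outcomes, "Key secondary continuous outcomes will be analysed using t-test or Wilcoxon rank-sum test depending on normality". The t-test branch is reported as a difference in means with a 95% CI. For the other branch, "Results from Wilcoxon rank-sum tests will be presented as differences in medians and p-values".

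The outcomes that can reach this branch are listed under the key secondary outcomes:
- Opioid use: "A cumulated amount of opioid in Morphine Milligram Equivalents within the first 6 hours postoperatively".
- Pain: "Pain levels (numerical relation scale (NRS) 0-10) during rest and activity (walking 5 meters) at 4 and 6 hours".
- Postoperative nausea and vomiting (PONV), scored on the same 0-10 scale at the same times.

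The 4- and 6-hour pain and PONV scores also get a mixed-effect model with patient as a random effect. Opioid MME gets no second analysis.

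**The concern.** There are two faults in one line. First, the Wilcoxon branch replaces the interval that the general rule promises with a p-value. Second, the estimate and the test need not agree. The rank-sum test addresses the probability that a value from one arm exceeds a value from the other, with ties counted as half. That corresponds to a difference in medians only if one distribution is the other moved sideways. The SAP does not state this assumption, and it is hard to defend for a bounded, tied 0-10 score or a skewed cumulative dose.

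Outcomes are sent to this branch because they are not normal, so it receives those for which a pure shift is least plausible. Each trial is sized only for the primary endpoint, at 32 evaluable and 37 recruited per arm. A non-significant secondary result without an interval does not let the reader tell no meaningful difference from too little data.

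**Working it through.** **No SAP figure is in dispute.** The only reproducible figure is the sample size: 60% vs 90%, two-sided 5%, 80% power, no continuity correction, gives 32 per arm (power 80.6%). With the allowance for dropout, 32 × 1.15 = 36.8, so 37. The checks below use 37 per arm. The SAP gives no distribution for pain, PONV or opioid MME, so every distribution here is an assumption.

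**1. The estimate and the test can disagree (one constructed data set).** NRS scores, 37 per arm.
- Arm A: four 0s, five 1s, six 2s, eighteen 3s, three 4s, one 5.
- Arm B: one 1, three 2s, seventeen 3s, six 4s, five 5s, three 6s, two 7s.
- Both medians (the 19th ordered value) are 3, so the difference in medians is 0.
- Of 37 × 37 = 1369 pairs, B is higher in 849, tied in 352 and lower in 168. U = 849 + 352/2 = 1025, against 684.5 expected under no difference.
- The tie-corrected SD is 87.24, so z = (1025 − 684.5 − 0.5)/87.24 = 3.90 and p = 0.0001.
- Mann-Whitney probability = 1025/1369 = 0.75. Hodges-Lehmann shift = 1, approximate 95% CI 0 to 2.

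The planned report would read: difference 0, p = 0.0001.

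**2. How often this happens for PONV.** Assumptions: zero-inflated 0-8 scores, two-sided rank-sum test at 5%, 4000 simulated trials of 37 per arm.

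| Any nausea | Test significant | Of those, median difference exactly 0 | Of those, Hodges-Lehmann shift exactly 0 |
|---|---|---|---|
| 15% vs 40% | 67% | 85% | 95% |
| 20% vs 50% | 76% | 38% | 70% |

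Repeat runs differ by a point or two. At 32 per arm the share with a median difference of 0 falls to 73% and 29%.

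The reason is simple. With 37 patients the median is 0 whenever 18 or fewer have any nausea. The chance of that is 0.89 at a true rate of 40% and 0.50 at 50%. Conditioning on a significant test lowers both somewhat.

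The Mann-Whitney probability does move. If non-zero scores are distributed alike in both arms, its true value is:
- 15% vs 40%: 0.40 × 0.85 + ½(0.60 × 0.85 + 0.40 × 0.15) = 0.625.
- 20% vs 50%: 0.50 × 0.80 + ½(0.50 × 0.80 + 0.50 × 0.20) = 0.65.

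**3. How often this happens for pain and opioid MME.** Assumptions: pain as rounded normal scores with SD 2 and means 3 vs 4, 4.5 or 5; opioids as skewed gamma totals with means 10 vs 20 or 15 vs 25 mg, including totals rounded to 5 mg. The median difference was exactly 0 in only about 1% to 3% of significant trials.

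**4. What else is planned for each outcome.** Pain and PONV have the mixed model, which yields a between-arm contrast, and the general CI rule applies to it. Opioid MME has nothing beyond the t-test or Wilcoxon line. If it is judged non-normal, its whole planned report is a difference in medians and a p-value.

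**The case against.** The strongest reply is that this is one reporting line for secondary outcomes, that medians beside a rank-sum p-value are a familiar descriptive summary, and that the SAP never claims the p-value tests the medians. That is fair. Under a pure location shift, the shift does equal the difference in population medians. So it would be too strong to say that the test never addresses the median difference. It does so only under an assumption that the SAP does not state.

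A reader might infer three further things that the document does not support:
- *That all key secondary outcomes lack a measure of precision.* Pain and PONV also have the mixed model, to which the general CI rule applies.
- *That a zero difference with a small p-value threatens every Wilcoxon outcome.* Under the assumptions tried, it is essentially a PONV problem.
- *That the Fisher outcomes show the same contradiction.* The SAP says "Key secondary dichotomous outcomes will be compared using fisher's exact test" and is silent on what is presented. The general rule already calls for an interval there and nothing contradicts it.

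What stands is the explicit wording for Wilcoxon results. There the specific instruction lists what is presented and leaves the interval out, while the adjoining t-test sentence includes it.

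**Conclusion.** The point holds as a minor reporting correction. The conflict between the two SAP sections is textual and needs no assumption. Its practical weight falls mainly on opioid MME, which would have no measure of precision if it goes to the Wilcoxon test. For PONV, the mismatch between estimate and test could be visible in about 38% to 85% of significant trials at 37 per arm. That range rests on assumed nausea rates and should not be carried over to pain or opioid totals, where about 1% to 3% was found. The primary outcome, its odds ratios and intervals, the sample size and the analysis population are all unaffected.

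**What to change.** In the analysis methods section, replace the wording on differences in medians and p-values as follows:
- **Opioid MME and pain:** the Hodges-Lehmann shift with its 95% CI, plus the rank-sum p-value. Medians and quartiles per arm can stay as description.
- **PONV:** the Mann-Whitney probability with a 95% CI, plus the p-value. The Hodges-Lehmann shift is not suitable here because it is also usually 0 (95% and 70% of significant runs above).

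The cost is a few words of SAP text and little code. R, the software named in the SAP, returns the Hodges-Lehmann interval from wilcox.test with conf.int = TRUE. No design or data-collection change is needed.

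There are two small downsides. The table grows, and pain and PONV carry a second effect measure beside the mixed-model contrast. On a heavily tied whole-number scale the Hodges-Lehmann interval is also approximate and its limits fall on whole points. In the constructed example it touches 0 although p = 0.0001, so the interval should be labelled approximate for pain.

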Each trial is conducted as a pragmatic, multicentre, randomized (1:1), single-blinded, clinical trial. Participants are randomized to receive either 1) spinal anaesthesia (SA) or 2) general anaesthesia (GA). Study data is gathered continuously during admittance. Study personnel is blinded to the allocation of the patients, but clinical personnel and the patients are not blinded, as this is not feasible given the interventions.

RCT SAGA UKA is conducted as a pilot trial exclusively at Copenhagen University Hospital Hvidovre. RCT SAGA THA and RCT TKA are conducted as multicentre trials at both Copenhagen University Hospital Hvidovre and Lillebaelt Hospital – Vejle.

RANDOMIZATION

Permutated block-randomization (4 or 6), stratified by centre for RCT SAGA THA and TKA, with allocation disclosed using non-transparent envelopes. A designated person, at Clinical Orthopaedic Research Hvidovre, Copenhagen University Hospital Hvidovre, with no other relation to the project is responsible for generating randomization sequences and preparation of the envelopes. Included patients are randomised at least three days before their planned surgery date.

SAMPLE SIZE

v. 1.0

The primary endpoint of the study is whether patients are able to be safely mobilized during a 5meter walking test within 6 hours of surgery. In previous studies safe mobilization was achieved after GA for 95% of THA and TKA patients, while it was only achieved for 30-45% of THA and TKA patients after SA. For this study we decided on a minimal clinically relevant difference in proportions of 30%. To detect a clinically relevant difference between 60% achieving safe mobilization in one group and 90% of achieving safe mobilization in the other group within 6 hours, would require 32 patients in each arm of each trial (95% confidence, 80% power). We aim to include 37 participants to each arm of each trial, to allow for a 15% dropout-rate in each trial.

- RCT SAGA UKA: 74 participants (37 SA and 37 GA) all from Copenhagen University Hospital Hvidovre.
- RCT SAGA THA: 74 participants (37 SA and 37 GA) from Copenhagen University Hospital Hvidovre (intended nr. participants = 38) and Vejle Hospital (intended nr. participants = 36).
- RCT SAGA TKA: 74 participants (37 SA and 37 GA) from Copenhagen University Hospital Hvidovre (intended nr. participants = 38) and Vejle Hospital (intended nr. participants = 36).

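### Fisher's exact test for fulfilment of discharge criteria is valid but conservative; Boschloo's exact test would gain roughly 0 to 8 points of power at the same 5% level

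*SAP*

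**What the plan says.** - SAP, Analysis Methods: "Key secondary dichotomous outcomes will be compared using fisher's exact test". The sentence does not say whether the test is two-sided, and it names no effect measure to go with the p-value.
- SAP, Key Secondary Outcomes, on discharge criteria: "This will be a dichotomous outcome where patients are either ready for discharge (fulfil all criteria) or are not ready for discharge". The other key secondary outcomes are pain and nausea scores and a cumulative opioid dose, so the Fisher sentence applies to this outcome alone.
- SAP, Confidence Intervals and P-values: "Confidence level is set at 95%, and results are presented with 95% confidence intervals", and "No adjustments for multiplicity are made".
- SAP, Sample Size, for the primary outcome only: a contrast of 60% with 90% safely mobilized is said to need 32 evaluable patients per arm at 80% power and 95% confidence. The recruitment goal then allows for losses: "We aim to include 37 participants to each arm of each trial, to allow for a 15% dropout-rate in each trial".
- SAP, Analysis Populations and Missing Data: some randomised patients may be left out of the modified intention-to-treat set, and outcomes may be missing. The analysed arms therefore need not be equal.

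**The concern.** Fisher's test conditions on both margins of the 2×2 table, while the design fixes only the arm sizes. With about 35 patients per arm the conditional distribution is coarse. The largest attainable p-value not above 0.05 is often well below it, so part of the nominal 5% goes unused. Boschloo's test takes Fisher's p-value as its statistic and raises the cut-off until the maximum type I error, over all common rates, is as close to 5% as it can be without exceeding it. Because its cut-off is never below 0.05, it rejects whenever Fisher's test rejects, and sometimes when Fisher's does not.

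What is at stake is power for the first-listed secondary objective in three small trials. The type I error is controlled under either test.

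**Working it through.** **Inputs.** From the SAP: 32 evaluable and 37 randomised per arm, 1:1 allocation, 95% confidence. Assumed: two-sided testing, and a 30-point difference in discharge rates with the lower rate between 10% and 60%. The SAP gives no discharge rates, so its 60% vs 90% for mobilization serves only as one illustrative pair.

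**The plan's own figure.** The pooled-variance formula is n = [1.960·√(2·p̄(1−p̄)) + 0.842·√(p₁(1−p₁)+p₂(1−p₂))]² / (p₂−p₁)². With p₁ = 0.6, p₂ = 0.9 and p̄ = 0.75 this gives (1.960·0.6124 + 0.842·0.5745)² / 0.09 ≈ 2.835 / 0.09 ≈ 31.5, so 32 per arm. Then 32 × 1.15 = 36.8, so 37. Both reproduce, but both concern the primary outcome, which is analysed by logistic regression. The SAP states no size or power for the Fisher test.

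**Method.** Full enumeration of both binomials. With p_F(x,y) the two-sided Fisher p-value for x and y successes:

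- Size: maximum over p of Σₓ Σᵧ b(x; n₁, p)·b(y; n₂, p)·1[p_F(x,y) ≤ c]
- Power: the same sum with p₁ for the first arm and p₂ for the second

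Fisher uses c = 0.05. Boschloo uses the largest c that keeps the maximum size at or below 5%: c = 0.0746 at 32/32 and 0.0806 at 37/37.

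**Results.** The first arm has the lower rate. The last column is the range of Boschloo's gain, in percentage points, over all 30-point differences examined.

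| Arms | Max size, Fisher | Max size, Boschloo | Power at 60% vs 90%, Fisher → Boschloo | Range of gain |
|---|---|---|---|---|
| 32/32 | 3.3% | 4.7% | 74.8% → 80.4% | 1.8–7.4 |
| 33/33 | 3.6% | 4.85% | 75.0% → 82.0% | 1.1–8.4 |
| 36/36 | 2.8% | 4.9% | 80.0% → 86.4% | 6.3–8.7 |
| 37/37 | 2.9% | 4.7% | 81.5% → 87.1% | 5.6–8.3 |
| 36/37 | 3.8% | 4.9% | 85.5% → 87.0% | about 1.5–4.5 |
| 33/35 | 3.8% | 4.7% | 80.3% → 82.2% | 0.7–6.6 |
| 32/34 | 4.0% | 5.0% | 80.5% → 83.3% | 1.2–4.3 |
| 31/33 | 4.1% | 4.9% | 78.8% → 81.8% | 1.4–4.6 |
| 32/31 | 4.3% | 4.6% | 76.1% → 79.1% | 0.0–3.0 |

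Other assumed rates:

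- 50% vs 80%: 64.4% → 71.8% at 32/32; 71.4% → 77.2% at 37/37.
- 40% vs 70%: 61.9% → 65.2% at 32/32 (gain 3.3); 66.0% → 74.1% at 37/37 (gain 8.1).
- 32/33: Fisher's maximum size is 4.6%, and at 40% vs 70% both tests have 68.5% power (gain 0.0).
- 35/37 at 40% vs 70%: 65.9% → 72.8% (gain 6.9).

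In the unequal pairs of the table, the median gain over the 30-point differences is 1.7 to 3.0 points. Fisher's power also depends erratically on balance: at 60% vs 90% it is 85.5% at 36/37 but 81.5% at 37/37, although the latter has one more patient. Boschloo's is 87.0% and 87.1%.

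**The case against.** The strongest reply is that nothing here is wrong. Fisher's test is standard and pre-specified, and it keeps the type I error at or below 5%. The outcome is secondary and was not separately powered. That stands, and it limits the point to an efficiency improvement.

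Three stronger readings are tempting, and the document supports none of them:

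- **A general loss of 6 to 8 points at a true level of 3%.** These figures belong to exactly equal arms, above all 37/37. Exclusions after randomisation and missing data make small imbalances likely. Fisher's maximum size then rises to about 4 to 4.6%, and the gain can fall to nothing. Even at 32/32 the gain is only 1.8 points at 35% vs 65%.
- **A missed power target.** Fisher's 74.8% at 32/32 for 60% vs 90% lies below 80%, but those rates, that sample size and that power were set for safe mobilization. The SAP promises no power for discharge criteria.
- **No interval planned for this outcome.** The SAP promises 95% intervals for results in general. Only the effect measure for this outcome is left unnamed, which is a small clarification.

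It is also fair to say that the replacement is not wholly without drawbacks. Boschloo's test is less familiar to readers. A score interval is not its exact inverse, so p-value and interval can occasionally disagree near the threshold.

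**Conclusion.** The point holds as a modest, free improvement. Fisher's test uses about 3% of the nominal 5% with equal arms of 32 to 37, and about 4 to 4.6% when the arms differ by one or two. Boschloo's test keeps the error at or below 5%, cannot be less powerful, and gains roughly 0 to 8 points for a 30-point difference: about 6 to 8 at 37/37, often 1 to 4 with unequal arms, and 8.7 at the most favourable pair examined (36/36). The sizes need no assumption about discharge rates. The power figures do, and they also assume two-sided testing and a 30-point difference. The ordering of the two tests depends on neither the rates nor the difference.

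**What to change.** In SAP, Analysis Methods, replace Fisher's test by a two-sided Boschloo exact test at the 5% level for fulfilment of discharge criteria, at 6 hours and, where compared, at 4 hours. In the same place, name the effect measure: the absolute difference in proportions (GA minus SA) with a 95% score interval (Miettinen–Nurminen). Leave the interval unstratified in all three trials. A centre-stratified interval beside an unstratified test would be two different procedures and would make disagreement between them more likely.

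Add that the p-value comes from the Boschloo test and that any disagreement with the interval near the threshold will be reported as such. The change should be made before allocation is disclosed to the analyst. It costs a sentence or two and an R package in the software already planned, with no extra patients or data. If the sponsor prefers to keep Fisher's test for familiarity, the analysis remains valid, and only the effect measure needs to be named.
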